1.3 SCHEDULE OF ACTIVITIES AND SAMPLE COLLECTION SCHEDULE

Table 1 Schedule of Activities

Visit	SCR ^a	Double-Blind Treatment							UV ^c	Early D/C Visit ^d	Safety Follow-Up Visit ^e
	1	2	3	4	5	6	7	8			16 (or 4 weeks after Early D/C)
Study week		0	2 ^b	4	6 ^b	8	10 ^b	12			
Window in Days	-28 to -1	NA	±2	±2	±2	±2	±2	±2	NA	NA	±2
Informed consent ^f	x										
Review of eligibility criteria	x	x									
Randomization		x									
Demographic data	x										
Medical history and baseline conditions	x										
Review of contraception methods	x	x		x		x		x	x	x	x
C-SSRS	x			x		x		x	x	x	x
Vital signs ^g	x	x		x		x		x	x	x	x
Weight		x						x		x	x
Height		x									
Complete physical examination ^h	x	x						x	(x)	x	
Neurological examination ⁱ	x	x						x	(x)	x	
Query for potential unreported relapses		x		x		x		x	x	x	x
EDSS ^j	x	x						x	(x)	x	
12-lead ECG ^k	x	x		x				x		x	
Blood tests: ^l											
Hematology and full chemistry panel	x	x		x		x		x	(x)	x	x

Table 1 Schedule of Activities (cont.)

Visit	SCR ^a	Double-Blind Treatment							UV ^c	Early D/C Visit ^d	Safety Follow-Up Visit ^e
	1	2	3	4	5	6	7	8			16 (or 4 weeks after Early D/C)
Study week		0	2 ^b	4	6 ^b	8	10 ^b	12			
Window in Days	-28 to -1	NA	±2	±2	±2	±2	±2	±2	NA	NA	±2
Limited chemistry panel: ALT, AST, total and direct bilirubin testing			x		x		x				
Hepatic synthetic function testing (PT, INR, aPTT)	x							x	(x)		
Lipids		x						x		x	
Flow cytometry ^m	x	x ⁿ		x		x		x		x	x
Total Ig, IgG, IgA, IgM	x			x		x		x		x	x
Hepatitis B screening ^o	x										
Hepatitis B virus DNA	x			(x)				(x)		(x)	
Hepatitis C screening ^p	x										
HIV screening	x										
Tuberculosis Test (QuantiFERON®-TB Gold)	x										
Plasma PK sample ^q		x		x		x		x	(x)	x	
Additional intensive PK sampling (optional) ^q		x		x							
Serum and plasma biomarkers ^r	x	x ⁿ		x		x		x		x	x
RNA collection (PAXgene tube)	x	x ⁿ						x		x	x
In clinic pregnancy test ^s	x	x		x		x		x	(x)	x	x
Urinalysis		x		x				x	(x)	x	x

Table 1 Schedule of Activities (cont.)

	SCR ^a	Double-Blind Treatment									Safety Follow-Up Visit ^e
Visit	1	2	3	4	5	6	7	8			
Study week		0	2 ^b	4	6 ^b	8	10 ^b	12	UV ^c	Early D/C Visit ^d	16 (or 4 weeks after Early D/C)
Window in Days	-28 to -1	NA	±2	±2	±2	±2	±2	±2	NA	NA	±2
CSF collection (optional) ^t	x							x			
MRI ^u	x			x		x		x	(x)	(x)	
Concomitant medications	x	x		x		x		x	x	x	x
Adverse events	x	x		x		x		x	x	x	x
Study treatment dispensation		x		x		x		x ^v			
Study treatment compliance				x		x		x		x	

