RBR: RNA, serum and plasma samples (optional) ^w	x	x ⁿ		x		x		x		x	x
RBR: DNA (optional) ^w		x ^x									

C-SSRS= Columbia-Suicide Severity Rating Scale; CSF= cerebrospinal fluid; DBT= double-blind treatment; D/C= discontinuation; eCRF = electronic Case Report Form; EDSS= Expanded Disability Status Scale; HBcAb= hepatitis B core antibody; HBsAg= hepatitis B surface antigen; Ig= immunoglobulin; MRI= magnetic resonance imaging; OLE= open-label extension; PK= pharmacokinetic; RBR= research biosample repository; SCR.= screening; TB= tuberculosis; ULN= upper limit of normal; UV= unscheduled visit; x required, (x) not always required.

Table 1 Schedule of Activities (cont.)

- ^a Participants are permitted one re-screening. As a general guideline, MRI scan, EDSS, RBR, hematology, chemistry, urinalysis, CD4, ECG, immunoglobulins, hepatitis B, C, HIV, hepatic synthetic function testing, lipids, flow cytometry, and TB screening and biomarkers samples should be repeated if there is more than 6 weeks between the screening *assessment date* and re-screening *assessment date*. All other procedures listed in the schedule of activities for the screening visit should be repeated at the re-screening visit. Any screening assessment may be repeated at a re-screening visit if judged by the investigator to be clinically necessary.
- ^b *It is preferred that the blood tests performed at these visits are analyzed by the central laboratory during a clinic visit. However, if these are performed by an accredited local laboratory, the results and reference ranges must be added to the appropriate adverse event eCRF form when applicable.*
- ^c UV may be performed, as clinically appropriate. It must be performed in the following situations: 1) if the patient is experiencing neurological worsening, 2) if the patient has $> 3 \times$ ULN AST or ALT, or 3) if the patient is experiencing symptoms that could be associated with worsening liver function. Assessments at UVs may be performed as clinically indicated. In the case of abnormalities in transaminase levels or clinical indications of worsening liver function, additional laboratory testing may be required per medical monitor guidelines (see Table A6-1).

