- ° Tests required for hepatitis B screening: HBsAg, total HBcAb, and viral DNA PCR. Participants with a positive HBsAg must be excluded. Participants with a positive HBcAb are permitted provided viral DNA PCR is negative. Participants with a positive HBcAb but negative HBV DNA PCR will have their hepatitis B viral DNA monitored as per the schedule of activities.
- ° Hepatitis C screening: HCAb must be negative.
- ° Please refer to [Table 3](#) for more details.
- ° Biomarker samples should be collected ± 3.5 days from MRI scan. Note: Not all biomarker samples will be collected at each MRI visit; however, those that are collected should be collected as close to the MRI scan as possible.
- ° All women of childbearing potential will have a serum pregnancy test at screening. Urine pregnancy tests will be performed at specific subsequent visits. If a urine pregnancy test is positive, it must be confirmed by a serum pregnancy test.
- ° The Day 1 CSF collection by lumbar puncture should only be performed once other screening tests confirm that the patient qualifies for the study. Lumbar puncture can be performed anytime during the screening period or at Day 1 prior to dosing. The Week 12 lumbar puncture should to be performed between 1 to 2 hours after the administration of study drug in clinic. A contemporaneous plasma PK sample should be collected at the time of CSF collection to enable comparison of CSF and serum drug levels. *If the Week 12 lumbar puncture is missed, it can be performed at a later visit, including an OLE visit.*
- ° MRI scans should be obtained as close to the scheduled visit as possible (± 3 days) and may be obtained at UV if medically warranted. MRI scan may not be performed earlier than 3 weeks after IV corticosteroid treatment for MS relapses. At the study D/C visit, an MRI scan should be obtained if an MRI scan was not performed during the prior 4 weeks.
- ° Study treatment will only be dispensed for participants continuing in the optional OLE.
- ° RBR: Not applicable at a site that has not been granted approval for RBR sampling. Performed only for patients at participating sites who have provided written informed consent to participate.
- ° A single, DNA sample will be collected for RBR at the baseline visit. If the DNA sample is not taken at Visit 2 (baseline), the sample may be taken at any subsequent timepoint during the trial.

Table 2 Schedule of Activities: Open-Label Extension Phase

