- ^g Includes an evaluation of the head, eyes, ears, nose, and throat and evaluation of the cardiovascular, dermatologic, musculoskeletal, respiratory, and gastrointestinal systems; genitourinary examinations may be performed if clinically indicated. A separate neurological examination should be performed by the treating physician if the treating physician is not performing the EDSS. During an UV, the neurological examination must be performed if the participant is experiencing neurological worsening between scheduled visits.
- ^h The EDSS can be performed by either the treating investigator or a separate examining investigator. The person performing the EDSS must have a valid Level C Neurostatus certification.
- ⁱ ECG recordings must be performed after the participant has been resting in a supine position for at least 10 minutes.
- ^j Participants should fast before the blood draws.
- ^k Participants with a positive HBcAb but negative HBV DNA PCR will have their hepatitis B viral DNA monitored as per the schedule of activities.
- ^l To be collected predose except for the UV and Early D/C visit where sample timing is flexible.
- ^m This sample is optional per the investigator's discretion
- ⁿ Biomarker samples should be collected ± 3.5 days from MRI scan. Note: Not all biomarker samples will be collected at each MRI visit; however, those that are collected should be collected as close to the MRI scan as possible.
- ^o Flow cytometry: Analysis may include, but is not limited to, the determination of B-cell and T-cell numbers and other lymphocyte subsets.

Table 2 Schedule of Activities: Open-Label Extension Phase (cont.)

- ^p All women of childbearing potential will have a serum pregnancy test at screening. Urine pregnancy tests will be performed at specified subsequent visits. If a urine pregnancy test is positive, it must be confirmed by a serum pregnancy test.
- ^q MRI scans should be obtained as close to the scheduled visit as possible (± 3 days) and may be obtained at an UV if medically warranted. MRI scan may not be performed earlier than 3 weeks after IV corticosteroid treatment for MS relapses. At the Study D/C visit, an MRI scan should be obtained if an MRI scan was not performed during the prior 4 weeks.
- ^r RBR: Not applicable at a site that has not been granted approval for RBR sampling. Performed only for patients at participating sites who have provided written informed consent to participate.

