- Any concomitant disease that may require chronic treatment with systemic corticosteroids or immunosuppressants during the course of the 12-week double-blind study period
- History of alcohol or other drug abuse within 12 months prior to screening
- Positive screening tests for active, latent, or inadequately treated hepatitis B (as evidenced by either of the following):
 - Positive hepatitis B surface antigen (HBsAg)
 - Positive hepatitis B core antibody [total HBcAb] with detectable hepatitis B virus (HBV) DNA
- Positive screening tests for hepatitis C (positive hepatitis C antibodies)
- Evidence of active or latent or inadequately treated infection with tuberculosis (TB) as defined by the following:
 - A positive QuantiFERON® TB-Gold (QFT) test is found at screening. QFT testing should be performed through the central laboratory (see [Table A2-1](#) for test requirements).
 - An indeterminate QFT test should be repeated.
 - A positive QFT test or two successive indeterminate QFT results should be considered a positive diagnostic TB test.
 - An indeterminate QFT test followed by a negative QFT test should be considered a negative diagnostic TB test.
- Abnormalities in hepatic synthetic function tests (e.g., PT, INR, aPTT) judged by the investigator to be clinically significant
- History of hospitalization or transfusion for a GI bleed
- Known bleeding diathesis
- Any condition possibly affecting oral drug absorption
- History of or currently active primary or secondary (non-drug-related) immunodeficiency, including known history of HIV infection
- Inability to complete an MRI scan (contraindications for MRI scan, including but not restricted to, pacemaker, cochlear implants, intracranial vascular clips, surgery within 6 weeks of entry in the study, coronary stent implanted within 8 weeks prior to the time of the intended MRI scan) or contraindication to Gd administration
- Any previous history of organ transplantation
- Any previous treatment with bone marrow transplantation or hematopoietic stem cell transplantation
- Adrenocorticotrophic hormone or systemic corticosteroid therapy within 4 weeks prior to screening or during the screening period

Inhaled and topical corticosteroids are allowed

- Receiving an unstable dosing regimen of proton pump inhibitors (PPIs) or H₂receptor antagonist (H₂RAs) during the screening phase and/or no plan to remain at a stable dose for the duration of study treatment

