Appendix 2: Clinical Safety Laboratory Tests

Table A2-1 Protocol-Required Safety Laboratory Assessments

Central Laboratory Tests

 • Hematology: WBC count, RBC count, hemoglobin, hematocrit, platelet count, and differential count (neutrophils, eosinophils, basophils, monocytes, lymphocytes, and other cells). • Chemistry panel (serum or plasma): bicarbonate or total carbon dioxide (if considered standard of care for the region), sodium, potassium, chloride, glucose, BUN or urea, creatinine, total protein, albumin, phosphate, calcium, total and direct bilirubin, ALP, ALT, AST, urate, and LDH, amylase, lipase, and GGT. • Coagulation: INR, aPTT, and PT • HIV serology: HIV-1 antibody/HIV-1/2 antibody/HIV-2 antibody • HBV serology: HBsAg, HBsAb, and total HBcAb for all individuals; HBV DNA for individuals with negative HBsAg and HBsAb tests and a positive total HBcAb test 
 Individuals with a positive quantitative HBV DNA at screening (must be <500 IU/mL per the eligibility criteria) will undergo additional HBV DNA tests as outlined in the schedule of activities (see Section 1.3). • HCV serology: HCV antibody for all individuals; HCV RNA for individuals with a positive HCV antibody test • Lipids: cholesterol, LDL cholesterol, HDL cholesterol, and triglycerides • Quantitative immunoglobulins: IgA, IgG, and IgM • Pregnancy test 
 All women of childbearing potential will have a serum pregnancy test at screening. Urine pregnancy tests will be performed at specified subsequent visits. If a urine pregnancy test is positive, it must be confirmed by a serum pregnancy test. • Urinalysis, including dipstick (pH, specific gravity, glucose, protein, ketones, and blood) and microscopic examination (sediment, RBCs, WBCs, casts, crystals, epithelial cells, and bacteria) • Tuberculosis test: QuantiFERON®-TB Gold 
 Note: This test should be performed at the central laboratory; however, in the event of extenuating circumstances and with Sponsor approval, an appropriately accredited local laboratory may be used, and Roche will collect the results.
Local Laboratory Tests

 • Urine pregnancy tests will be performed at screening and specified subsequent visits. If a urine pregnancy test is positive, it must be confirmed by a serum pregnancy test.

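### The hepatitis B entry in Table A2-1 contradicts Section 5.2 and the schedule of activities on the DNA limit, on who is tested and on who is monitored

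*Protocol*

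**What the plan says.** Three places in the protocol give one consistent hepatitis B rule.

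- **Section 5.2 (Exclusion Criteria)** excludes a positive HBsAg and, separately, "Positive hepatitis B core antibody [total HBcAb] with detectable hepatitis B virus (HBV) DNA". No concentration is stated.
- **Section 1.3, Table 1 footnote** sets the screening panel: "Tests required for hepatitis B screening: HBsAg, total HBcAb, and viral DNA PCR". On entry it says: "Participants with a positive HBcAb are permitted provided viral DNA PCR is negative". In the table body, the row "Hepatitis B virus DNA" carries an x at screening and a bracketed x at Week 4, Week 12 and early discontinuation. The key reads "x required, (x) not always required".
- **The Table 1 footnote and the Table 2 (open-label extension, OLE) footnote** both name who is followed: "Participants with a positive HBcAb but negative HBV DNA PCR will have their hepatitis B viral DNA monitored as per the schedule of activities".

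Appendix 2, Table A2-1, the list of protocol-required safety laboratory tests, says something else. Its HBV line calls for HBsAg, HBsAb and total HBcAb in everyone, then "HBV DNA for individuals with negative HBsAg and HBsAb tests and a positive total HBcAb test". It goes on: "Individuals with a positive quantitative HBV DNA at screening (must be <500 IU/mL per the eligibility criteria) will undergo additional HBV DNA tests", with a pointer to the schedule of activities.

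**The concern.** The table attributes to the eligibility criteria a DNA ceiling that they do not contain, makes DNA testing conditional where the schedule does not, and assigns follow-up to a group that cannot be in the trial.

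This would be a minor drafting matter if Table A2-1 were background text, but it is operational. Section 8.2.4 treats Appendix 2 as the place where the protocol-required laboratory assessments are defined. The introduction to Appendix 2 says that the central laboratory performs the tests in the table. The reflex rule (run DNA only if certain antibody results occur) appears nowhere else in the protocol.

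If a laboratory set up its reflex testing from this entry, an HBcAb-positive, HBsAb-positive candidate could reach randomization without the DNA result that Section 5.2 needs. If a site relied on it, low-level viraemia could be taken as acceptable before an immunomodulatory drug is started. Appendix 6 lists both infection and transaminase elevation among the drug's risks, so an unrecognised hepatitis B infection would also make a liver signal harder to attribute.

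**Working it through.** No sample size, power or error rate is involved. The check is a comparison of the texts, followed by a count of the cases in which they disagree.

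**Step 1. The texts side by side**

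| Point | Section 5.2 and Tables 1 and 2 | Table A2-1 |
|---|---|---|
| DNA level that excludes an HBcAb-positive person | Any detectable level | Implied 500 IU/mL or more |
| Who has DNA measured at screening | Everyone screened; no HBsAb condition | Only HBsAg-negative, HBsAb-negative, HBcAb-positive |
| Who has DNA followed on study | HBcAb-positive, DNA-negative | DNA-positive at screening |

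On the first row, the 500 IU/mL figure appears only in Table A2-1, so its reference to the eligibility criteria leads to a criterion that does not exist.

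On the third row, everyone whom Table A2-1 sends for DNA testing is HBcAb-positive. A positive result in that group is an exclusion under Section 5.2. The group named for follow-up therefore cannot be enrolled, and the group that should be followed is not named. Section 5.2 makes detectable DNA exclusionary only together with HBcAb positivity, but this does not rescue the table, because it tests no HBcAb-negative person.

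**Step 2. Count over the possible profiles**

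Take HBsAg-negative, HBcAb-positive candidates. Cross HBsAb (2 levels) with DNA (negative; detectable below 500 IU/mL; 500 IU/mL or more): 2 × 3 = 6 profiles. Two readings are assumed: Table A2-1 is read alone, and its requirement of less than 500 IU/mL means exclusion at or above that value.

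| HBsAb | DNA | Governing text | Table A2-1 alone | Same? |
|---|---|---|---|---|
| − | negative | tested, enters, monitored | tested, enters, not monitored | no |
| − | <500 | tested, excluded | tested, enters, monitored | no |
| − | ≥500 | tested, excluded | tested, excluded | yes |
| + | negative | tested, enters, monitored | not tested, entry undetermined, not monitored | no |
| + | <500 | tested, excluded | not tested, entry undetermined | no |
| + | ≥500 | tested, excluded | not tested, entry undetermined | no |

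- DNA tested: 6 of 6 under the governing text, 3 of 6 under Table A2-1.
- DNA monitored: 2 profiles under the governing text (rows 1 and 4), 1 under Table A2-1 (row 2), overlap 0.
- Handled differently in at least one respect: 6 − 1 = 5 of 6.

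These are logical cases, not people. The documents give no HBcAb prevalence, so the number of affected candidates cannot be estimated.

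**Step 3. Which text governs**

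Table A2-1 itself defers to the eligibility criteria and the schedule, and Section 8.2.4 requires the Appendix 2 tests to follow the laboratory manual and the schedule. Section 5.2 and the footnotes to Tables 1 and 2 agree with one another. Table A2-1 is the outlier.

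**The case against.** The strongest reply is that the table sends its reader to the right rule. Anyone who follows either pointer in the entry reaches Section 5.2 or the schedule and finds the stricter condition. Sections 6.3.1 and 8 require screening to be complete and eligibility established before assignment, and waivers are not permitted. An HBcAb-positive candidate without a DNA result has incomplete screening, and enrolling someone with detectable DNA would be a protocol violation. On this view it is a stale appendix entry. The same table also reflexes HCV RNA in antibody-positive people, who are already excluded, which suggests template text that was never tailored (an inference).

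There are backstops as well: exclusion for ALT or AST above 2 × ULN; ALT/AST every two weeks in the double-blind phase; HBV DNA at Weeks 4 and 12 and in the OLE for HBcAb-positive, DNA-negative participants; and mandatory discontinuation for active hepatitis B.

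Much of this stands. It settles which text governs and makes harm conditional on someone following the table. The profile count also adds no weight of its own: three of its five differences come from the single HBsAb clause, and the count only restates the three discrepancies.

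It does not make the entry harmless. A laboratory working from its own test list has no cue that the quoted limit is wrong. The screening ALT/AST limit does not replace a DNA result, and the on-treatment safeguards act only after exposure. The HBV DNA monitoring backstop is itself one of the items that Table A2-1 misdirects. In the OLE, which may last 192 weeks, scheduled chemistry falls to every 12 weeks after Week 24, so directing DNA follow-up to the right people matters more there.

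**Conclusion.** The concern holds. All three contradictions are in the current protocol text and are not explained by redaction or by how the document was extracted. The error is confined to one entry in Table A2-1; Section 5.2 and the footnotes to Tables 1 and 2 are sound.

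It should be fixed as a matter of participant safety and eligibility. It does not affect the design, sample size, endpoints or efficacy analysis. Whether it has had any practical effect depends on the laboratory manual and the central laboratory's reflex setup, neither of which is in the documents. Nothing in them shows that any participant was misclassified.

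**What to change.** Amend the HBV entry in Table A2-1 only:

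1. Delete the 500 IU/mL text.
2. Require HBV DNA PCR at screening as in Table 1, without an HBsAb condition. Testing every HBcAb-positive candidate regardless of HBsAb would be enough to apply Section 5.2, but it would still be narrower than the Table 1 footnote, so full alignment is better.
3. State that HBcAb-positive, DNA-negative participants have HBV DNA followed on the schedule of activities.

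Then check the laboratory manual and the central laboratory's reflex rule against the corrected entry. List all enrolled HBcAb-positive participants with their screening HBV DNA result, and confirm that each is negative.

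The cost is one table entry, one check of the laboratory setup and one listing.
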